Investigational medicinal product(s)	
Brodalumab: 210 mg brodalumab in 1.5 mL solution for subcutaneous injection (140 mg/mL). Each kit contains 2 syringes.
 
Fumaric acid esters: 30 or 120 mg Fumaric acid tablets for oral administrations. Fumaderm® Initial package contains 40 tablets of 30 mg and Fumaderm® package contains 70 tablets of 120 mg.

TRIAL ID: LP0160-1327	DATE: 17-APR-2018	VERSION: 4.0 PAGE 21 OF 108
-----------------------	-------------------	--------------------------------

Duration of treatment	Screening period up to 28 days, treatment period of 24 weeks, and follow-up period is 8 weeks for brodalumab and 2 weeks for fumaric acid esters (approximately 5 half-lives for each).
Number of subjects	A maximum of 204 subjects will be randomly assigned to study treatment such that more than approximately 102 evaluable subjects complete the trial.
Number of trial sites	Approximately 30 clinical sites in Germany
Statistical methods	
The co-primary endpoints PASI 75 and sPGA (0 or 1) at Week 24 (end of treatment visit) will be evaluated on the FAS.
 
Estimates and 95% confidence intervals (CI) for the response rates and treatment differences will be presented. The differences in response rates between treatment groups will be analysed using the Cochran-Mantel-Haenszel test and weight (<math>\geq 100</math> kg or <math>< 100</math> kg). The null hypotheses of no difference in response rates between brodalumab and fumaric acid esters will be tested against the two-sided alternative that there is a difference on a 5% level. Subjects who drop-out of the trial before Week 24 (end of treatment visit) will be regarded as non-responders.
 
As supportive analyses for the co-primary endpoints, a logistic regression model with baseline PASI or sPGA and weight group will be performed, and further, the mixed model for repeated measurements (MMRM) for PASI described below will be used to predict PASI 75 for subjects without assessments at Week 24 for an additional Cochran-Mantel-Haenszel analysis. Finally subjects who drop-out of the trial before Week 24 will be LOCF imputed and analyzed using the Cochran-Mantel-Haenszel test.
 
The trial is considered a success if superiority is confirmed for both primary endpoints.

Coordinating investigator	[name], [name]. med.
Sponsor	LEO Pharma A/S, [name]

[figure not shown]

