1) Subjects must be randomised within 28 days after screening or as soon as all inclusion and exclusion criteria are confirmed. Allow time for results from screening samples to be available from central lab.

2) An unscheduled visit can be performed before the follow-up visit for the following purposes: By individual need at the discretion of the investigator, AE follow-up (and related concomitant medication/procedures, if applicable), re-instructing the subject in procedures for home treatment with the investigational medicinal product, re-collection of blood and/or urine samples in case of medical need of following up on specific test abnormalities, suspicion of pregnancy, or in case of sampling or testing errors necessitating the collection of new samples. Procedures are marked in brackets "(x)" since they are optional depending on the reason for the unscheduled visit.

- 3) Subjects, who are withdrawn from the trial or discontinues trial treatment for any reason, should attend an early termination visit as soon as possible after last dose to have all early termination assessments performed. All mandatory assessments applicable for an early termination visit are marked with an asterix (\*). If a subject discontinues trial treatment or withdraws at a visit, then all mandatory assessments for an early termination visit must be performed at this particular visit.
- 4) Follow-up visit should be conducted no sooner than approximately 5 half-lives after the last administration of investigational medicinal product. Hence,
  - at 8 weeks ( $\pm 3$  days) after Week 24 or early termination visit for subjects allocated to brodalumab; and
  - at 2 weeks ( $\pm 3$  days) after Week 24 or early termination visit for subjects allocated to fumaric acid esters.Additional follow-up visit(s) should be performed only in case an AE is ongoing at the initial follow-up visit and is either a non-serious AE classified as possibly or probably related to investigational medicinal product or an SAE. No data will be collected at the additional follow-up visit(s). Where the (sub)investigator considers it appropriate, any additional follow-up visit(s) may be performed as a telephone contact.

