### 6.2.2 Fumaric acid esters

Fumaric acid esters have been used to treat psoriasis since 1959. An oral preparation containing dimethyl fumarate and monoethyl fumarate salts, Fumaderm®, is licensed in Germany for treating adults with moderate to severe plaque psoriasis in whom topical therapy is not effective. It is available in two strengths, Fumaderm® Initial containing 30 mg dimethyl fumarate per tablet and Fumaderm® containing 120 mg dimethyl fumarate per tablet.

Systemic therapy with fumaric acid esters is based on an established dosing scheme with a gradual increase to improve tolerability, especially with regards to gastrointestinal side effects. The dose is adjusted on an individual basis according to the response to therapy and the occurrence of side effects.

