## 7 Trial objectives and endpoints

### Panel 3 Objectives and endpoints

Objectives	Endpoints
Primary objective	
To compare the efficacy of subcutaneous injections of brodalumab to oral administration of fumaric acid esters in subjects with moderate to severe plaque psoriasis who are naive to systemic treatment.	
Co-primary endpoints:
 
 
At least 75% improvement from baseline at Week 24 in Psoriasis Area and Severity Index (PASI)
 
Static Physician's Global Assessment (sPGA) scale score of 0 or 1 at Week 24
 
 
Secondary endpoints:
 
 
At least 90% improvement from baseline at Week 24 in PASI
 
100% improvement from baseline at Week 24 in PASI
 
Change from baseline at Week 24 in PASI score
 
PASI improvement (%) from baseline at Week 24
 
Change from baseline at Week 24 in affected body surface area (BSA)
 

Secondary objectives	
To compare the effect on patient reported outcomes of subcutaneous injections of brodalumab to oral administration of fumaric acid esters in subjects with moderate to severe plaque psoriasis.	
Secondary endpoints:
 
 
Psoriasis Symptom Inventory (PSI) responder at Week 24 (total score <math>\leq 8</math>, with no item scores <math>> 1</math>)
 
PSI total score of 0 at Week 24
 
Number of symptom-free days from randomisation to Week 24 (symptom-free day = daily total PSI of 0 on that day)
 
Burden of symptoms assessed as the normalised area under the curve (AUC) of PSI from baseline to the last available assessment
 
Change from baseline at Week 24 in Dermatology Life Quality Index (DLQI) total score
 
DLQI total score of 0 or 1 at Week 24
 

To evaluate the safety and tolerability of subcutaneous injections of brodalumab versus oral administration of fumaric acid esters in subjects with moderate to severe plaque psoriasis.	
Secondary point:
 
 
Frequency of AEs and SAEs by preferred term
 

Exploratory objective	

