**Follow-up phase (Week 24 to Week 26/32)**

The follow-up visit is scheduled approximately 5 half-lives after last administration of IMP.

- If treated with brodalumab, the follow-up visit is scheduled at Week 32 (8 weeks after the end of treatment visit at Week 24).
- If treated with fumaric acid esters, the follow-up visit is scheduled at Week 26 (2 weeks after the end of treatment visit at Week 24).

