**8.3 Scientific rationale for trial design**

Randomised treatment allocation is applied as a methodology to reduce confounding by equalising factors (independent variables) not accounted for in the experimental design.

Open-label treatment with blinded efficacy assessment is applied since the route of administration differs, and since the complexity of applying double dummy blinding is considered inappropriate due to the individual dose adjustment scheme of fumaric acid esters. A blinded assessor will perform all efficacy assessment not knowing the assigned treatment, while the investigator will be unblinded. The investigator is unblinded since dose adjustment may be necessary for subjects randomised to fumaric acid esters.

A parallel design is applied to ensure correct temporal evaluation and to avoid any carry over effect from one treatment period to another, acknowledging the fact that, especially for biologic treatments, the effect may continue for weeks to months after treatment cessation.

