## **8.4 End of trial definition**

A subject is considered to have completed the trial if they have completed all periods of the trial, including the follow-up visit scheduled at Week 32 for brodalumab and at Week 26 for fumaric acid esters. The End of Trial Form must be completed for all randomised subjects. The filled form includes date of last dose, last attended scheduled visit number, and primary reason for withdrawal, if applicable.

The end of the trial is defined as the date of the last visit of the last subject in the trial.

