### 13.3.8.1 Adverse events

AEs will be coded during the trial according to the most recent version of Medical Dictionary for Regulatory Activities (MedDRA). All AEs will be presented by preferred terms (PT) and primary system organ class (SOC).

Treatment-emergent AEs (TEAEs) will be summarised, however, all AEs recorded during the course of the trial will be included in the subject data listings. An event will be considered treatment-emergent if started on or after the first day of IMP and no later than 5 half-lives after the last day on randomised treatment, or if started before the first use of IMP and worsened in severity thereafter. The tabulations described in the following will only include the treatment-emergent events.

An overall summary of the number of subjects with any TEAEs, the percentage of subjects with at least one event, the number of events and the event rate per 100 years will be presented. These summaries are done by SAEs, discontinuations from the trial due to AEs, treatment-related AEs, severe AEs, relation to device, outcome and AESIs.

Where there are several recordings of a specific AE within a subject, severity will be taken as the most severe recording for that specific AE. If a subject experience more than one AE of the same type, all severity evaluations should be recorded.

Where there are several recordings of causal relationship to a specific AE within a subject, causal relationship will be taken as the most-related recording from the last report of that AE.

Related AEs are defined as AEs for which the (sub)investigator has not described the causal relationship to IMP as 'not related'.

Summary tables based on SOC and PT are made for all TEAEs, serious TEAEs, related AEs, severe TEAEs, TEAEs reported as AESIs, AEs leading to withdrawal, and TEAEs with preferred term that are experienced by at least 5% of the subjects in any treatment arm or by at least 5% of all subjects.

Finally, relevant AE listings will be created.

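### Preferred-term AE tables compare about 30 to 32 weeks of observation on brodalumab with 26 on fumarates, with no common cut-off and no stated time-adjusted rate

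*Combined protocol and SAP*

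**What the plan says.** - **Objective and endpoint.** The safety objective in Panel 3 is comparative: "To evaluate the safety and tolerability of subcutaneous injections of brodalumab versus oral administration of fumaric acid esters". Its endpoint, repeated in section 13.3.4, is how often AEs and SAEs occur at preferred-term level.
- **Window.** Under section 13.3.8.1 an event counts if it starts on or after the first day of IMP and "no later than 5 half-lives after the last day on randomised treatment", or if it began earlier and worsened. The tabulations contain only these events.
- **Length of the window.** The protocol summary (Duration of treatment) states: "follow-up period is 8 weeks for brodalumab and 2 weeks for fumaric acid esters (approximately 5 half-lives for each". Section 12.1 collects AEs to Week 32 on brodalumab and Week 26 on fumarates.
- **Statistics shown.** Section 13.3.8.1 gives an event rate per 100 years for the overall TEAE summary and its categories (SAEs, discontinuations due to AEs, related, severe, device-related, outcome, AESIs). It lists the SOC and preferred-term tables without naming their statistics. The default for categorical data in section 13.3.10 is number and percentage of subjects.
- **Where the window starts.** Note 4 to Panel 2 says: "Follow-up visit should be conducted no sooner than approximately 5 half-lives after the last administration of investigational medicinal product". Section 8.1, however, sets the brodalumab visit from the end of treatment visit: "the follow-up visit is scheduled at Week 32 (8 weeks after the end of treatment visit at Week 24". Panel 5 marks the last brodalumab injection at Week 22 and none at Week 24.

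**The concern.** The tables that answer the comparative safety objective count events over a longer period in one arm. If an event keeps occurring after treatment stops, the arm observed longer shows the higher percentage even when weekly risk is the same. The rate per 100 years in the overall summary does not correct individual preferred terms, and its person-time denominator is not defined.

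The plan compares like with like elsewhere: vital signs and laboratory changes are taken from baseline to Week 24 in both arms (sections 13.3.8.3 and 13.3.8.4), and the PSI AUC is normalised for unequal duration (section 13.3.7). The AE tables are the exception. The window can also affect which terms appear in the table of events reaching 5% in an arm.

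**Working it through.** **Inputs from the protocol.** Treatment 24 weeks; post-treatment window about 8 v 2 weeks (summary); last brodalumab injection at Week 22 (Panel 5); planning dropout 50% on fumarates and below 40% on brodalumab (section 13.1; 40% is used here as the ceiling).

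**Assumptions, because the protocol gives no figure.** Equal weekly hazard h in both arms on treatment; post-treatment hazard k×h, with k from 0 to 1; dropout times uniform over 0–24 weeks; a share φ of dropouts followed for their full window, with φ from 0 to 1.

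**1. The protocol's own windows.** Brodalumab 24 + 8 = Week 32; fumarates 24 + 2 = Week 26. Both match section 8.1. Counted from the last injection, brodalumab ends at 22 + 8 = Week 30.

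**2. Completers, rare events.** The ratio is (24 + 8k)/(24 + 2k) for a Week 32 end and (24 + 6k)/(24 + 2k) for a Week 30 end.

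| k | Week 30 end | Week 32 end |
|---|---|---|
| 0 | 1.00 | 1.00 |
| 0.25 | 1.04 | 1.06 |
| 0.5 | 1.08 | 1.12 |
| 1 | 30/26 = 1.15 | 32/26 = 1.23 |

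**3. Completers, more common events, k = 1.** With 24-week risk p, the risk over w weeks is 1 − (1 − p)^(w/24). For p = 10%: 10.8% at 26 weeks, 12.3% at 30, 13.1% at 32. The ratio shrinks as events become common: 1.12–1.18 at p = 30%, 1.07–1.10 at 70%, 1.03–1.04 at 90%.

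**4. Display threshold, k = 1.** A term reaching 5% over the brodalumab window would stand at 1 − 0.95^(26/32) = 4.1% or 1 − 0.95^(26/30) = 4.3% over 26 weeks. It could be listed because of the window alone.

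**5. Planning dropout, rare events, k = 1.** Mean time on treatment is 0.6×24 + 0.4×12 = 19.2 weeks on brodalumab and 0.5×24 + 0.5×12 = 18.0 on fumarates, a ratio of 1.07. Mean observed weeks:

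| φ | Brodalumab (Week 30 / Week 32 end) | Fumarates | Ratio |
|---|---|---|---|
| 1 | 25.2 / 27.2 | 20.0 | 1.26 / 1.36 |
| 0.5 | 24.0 / 25.6 | 19.5 | 1.23 / 1.31 |
| 0 | 22.8 / 24.0 | 19.0 | 1.20 / 1.26 |

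Dividing out the 1.07 for time on treatment leaves a window effect of 1.13 to 1.28.

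**6. Would rates over the full window be enough?** No. For events confined to treatment, completers would give (24/32)/(24/26) = 26/32 = 0.81, or 26/30 = 0.87, in brodalumab's favour with no true difference.

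**7. Test of a common window** (first dose to the Week 24 or early termination visit), planning dropout, true ratio 1:

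| Measure | Risk in Weeks 0–8 only | Confined to treatment | Fully continuing |
|---|---|---|---|
| Planned-window n (%) | 1.02 | 1.07 | 1.20–1.36 |
| Full-window rate | 0.75–0.85 | 0.78–0.89 | 1.00 |
| Common-window n (%) | 1.02 | 1.07 | 1.07 |
| Common-window rate | 0.95 | 1.00 | 1.00 |

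The early-risk column uses mean at-risk time of 0.6×8 + 0.4×6.67 = 7.47 weeks v 0.5×8 + 0.5×6.67 = 7.33, where 6.67 = (2/3)×8 + (1/3)×4 is the mean for a dropout. The common-window pair spans 0.95–1.07; the other two measures together span 0.75–1.36. In completers both common-window measures are 1.00 in all three cases.

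**The case against.** **The plan is silent, not wrong.** The preferred-term tables are listed without a metric, so crude percentages follow only from the general default. Section 13.3.10 provides for a statistical analysis plan update before the code is broken, where contents could be settled. That is fair, and it is the right place for the fix. Nothing in the current text, however, supplies a common cut-off or a preferred-term rate.

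**The window is principled.** Five half-lives is one rule for both arms, and section 8.3 notes that with biologics "the effect may continue for weeks to months after treatment cessation". This stands, and those tables should stay.

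**The effect is small.** In the 10% example the excess is 1.5 to 2.3 percentage points, about 2 subjects of 102, against a standard error near 4.5 points. At half the post-treatment risk it is 11.2–11.6% v 10.4%, about one subject. This also stands and limits the importance of the point.

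**The larger ratios include differential dropout.** True: the window alone accounts for 1.04 to 1.23 in completers for k from 0.25 to 1. The low end under dropout also depends on how the gap between last injection and exit is modelled: 1.26 if two weeks are removed for every dropout, 1.28 if one week is removed on average.

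**Week 32 is the natural reading.** Perhaps, since the treatment phase runs to Week 24 and follow-up is set at Week 32. But Panel 2 note 4 counts from last administration, so the anchor needs stating.

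**The common window is not perfectly common.** Under planning dropout it still averages 19.2 v 18.0 weeks and leaves n (%) at 1.07. It removes the post-treatment imbalance, not differential dropout, which is why a rate is needed beside it.

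**Conclusion.** The concern holds. As written, the preferred-term tables compare 30–32 weeks with 26 in completers. With equal weekly risk the spurious ratio is 1.00 for events confined to treatment and up to 1.15–1.23 if risk continues fully after treatment. Under planning dropout with fully continuing risk it is 1.20–1.36, of which 1.07 is longer time on brodalumab. If brodalumab dropout were 20% (an assumption, not a protocol figure), it would be 1.38–1.48 with all dropouts followed, of which 21.6/18.0 = 1.20 is time on treatment.

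These sizes rest on assumed post-treatment risk, dropout timing and follow-up of dropouts. The unequal window itself does not. The tables are descriptive, the bias runs against brodalumab, and no primary test or success criterion changes. The importance is minor to moderate, and the change is worth making because it is cheap.

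**What to change.** In section 13.3.8.1 or the statistical analysis plan update:

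1. Add supplementary between-arm SOC and preferred-term tables on one window, from first dose to the Week 24 or early termination visit, or to the last dose date if neither visit took place. Show n (%) and the event rate per 100 patient-years, with person-time over that same window.
2. Define the person-time denominator of every rate per 100 years so that it matches the window in which its events are counted.
3. State whether the treatment-emergent window runs from the last dose or from the end of treatment visit.
4. Keep the five-half-life tables for both arms beside the new ones, with window lengths in a footnote, so that post-treatment events, including SAEs and AESIs, stay visible.

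**Cost.** One extra table set, two definitions and a footnote. AE start dates and visit dates are already collected, and section 8.4 covers the last dose: "The filled form includes date of last dose, last attended scheduled visit number".

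**Downside.** Person-time rates can mislead when events cluster early. That is plausible for fumarates, whose up-titration follows an "established dosing scheme with a gradual increase to improve tolerability, especially with regards to gastrointestinal side effects". If risk is confined to Weeks 0–8, the common-window rate ratio is 0.95 and the n (%) ratio 1.02 under planning dropout (0.88 and 1.05 at 20% brodalumab dropout). Percentages and rates should therefore be read together.

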### 13.3.8.2 Other specific safety assessments

Adverse events reported as injection site reactions will be summarised separately based on SOC and PT. Furthermore, a corresponding list will be created.

### **13.3.8.3 Vital signs and physical examinations**

The change in vital signs (BP, heart rate, body temperature and respiration rate) from baseline to Week 24 will be summarised as mean, standard deviation (SD), median, minimum and maximum values for each treatment group.

Furthermore, a shift table for vital signs showing the change from baseline to Week 24 in clinical assessments (normal; abnormal, not clinical significant; abnormal, clinical significant) will be performed.

Finally, a shift table for physical examinations (general appearance, lymph nodes and dermatologic examination) showing the change from baseline to Week 24 in clinical assessments (normal; abnormal, not clinical significant; abnormal, clinical significant) will be performed.

### **13.3.8.4 Clinical laboratory evaluation**

The change in each of the laboratory parameters from baseline to Week 24 will be summarised as mean, SD, median, minimum and maximum values for each treatment group.

Laboratory parameters will be classified as 'low', 'normal' or 'high', depending on whether the value is below, within or above the reference range, respectively. A shift table will be produced showing the categories at baseline against those at Week 24. Subjects with laboratory parameters outside the reference range will be listed.

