- 5) All visit-dates should be scheduled relative to the baseline visit, except for the follow-up visit which should be scheduled relative to the date of end of treatment visit (captured at Week 24 or at an early treatment withdrawal visit) and the investigational medicinal product (see note 4).
- 6) Informed consent must be signed both by subject and (sub)investigator (medically qualified) before any trial related procedures are carried out.
- 7) Re-evaluation of in-/exclusion criteria, including review of results from the central laboratory of screening samples.
- 8) At screening, all subjects will receive information that if they are randomised to brodalumab they will have to self-administer the subcutaneous injections. The subjects must confirm that he/she or the subject's designated person will be able to administer the subcutaneous injections that randomisation to brodalumab would entail.
- 9) The 2 first administered brodalumab doses, at baseline and Week 1, should be administered by the subject or designated person at the clinical trial site under supervision of the investigator or delegated person. After Week 1, IMP should be administered at home by subject or the subject's designated person (subcutaneous injection if randomised to brodalumab and oral administration if randomised to fumaric acid esters).
- 10) The DLQI should be completed by the subject prior to all other trial procedures and the electronic self-rated version, columbia-suicide severity rating scale (eC-SSRS) and the patient health questionnaire-8 (PHQ-8) should be completed after all other assessments have been performed.
- 11) Serum beta hCG test must be done in female subjects of childbearing potential (must also be done at visits after screening if a urine test is positive for pregnancy).
- 12) Sodium, potassium, magnesium, bicarbonate, albumin, blood urea nitrogen (BUN), creatinine, uric acid, total bilirubin, direct bilirubin, Alk phosphatase, aspartate aminotransferase (AST), alanine aminotransferase (ALT), and C-reactive protein (CRP).
- 13) RBC (red blood cell count), haemoglobin, haematocrit, platelets, white blood cell count (WBC), and differential (absolute count and %): neutrophils, lymphocytes, monocytes, eosinophils and basophils.
- 14) Specific gravity, pH, occult blood, protein, glucose, leucocyte esterase, ketones, and urine pregnancy test.

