### **9.5.2 Early termination assessments**

Subjects who are withdrawn or discontinues trial treatment for any reason, should attend an early termination visit as soon as possible after last dose, to have all early termination assessments performed. Early termination assessments are identical to the assessments scheduled for the end of treatment visit (Week 24).

If a subject discontinues IMP or withdraws from trial at a site visit, then this visit should be converted into an early termination visits and all applicable early termination assessments must be performed. The early termination is captured in the eCRF as an unscheduled visit by selecting the early termination option.

The subjects should attend a follow-up visit 8 weeks after the early termination visit for brodalumab or 2 weeks after the early termination visit for fumaric acid esters. The investigator will review and follow up any AEs according to Section [12.5](#).

If a subject withdraws from the trial, he/she may request destruction of any samples taken that are not tested, and the investigator must document this in the site's trial records.

Reason(s) for discontinuation must be recorded in the medical records and the eCRF (lack of efficacy, AE, withdrawal by subject, lost to follow-up, death, other).

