### **13.3 Statistical analysis**

#### **13.3.1 Disposition of subjects**

A subject disposition will be made including information of number of subjects screened, randomised, exposed, completing and withdrawn (and reason for withdrawal), by treatment group and in total. This will also include number of subjects included in the FAS and safety analysis set, by treatment group and in total.

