#### **13.3.3 Exposure and treatment compliance**

Relevant exposure, compliance and drug accountability data will be tabulated.

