### **13.3.10 General principles**

All statistical analyses of efficacy endpoints will be based on the FAS and safety endpoints on the safety analysis set (SAS). All significance tests will be two-sided using the 5% significance level. All CIs will be presented with 95% degree of confidence. No corrections for multiplicity will be performed.

If not mentioned otherwise, endpoints will be summarised descriptively at each visit by treatment and in total.

An observed-cases approach will be used for tabulations of data by visit (i.e. involving only those subjects who attended each specific visit). For categorical endpoints number of subjects not attending each specific visit will also be added.

Categorical data will be summarised using the number and percentage of subjects in each category. Continuous data will be summarised using the mean, median, SD, minimum, and maximum values.

In general, for endpoints evaluated as change from baseline and/or where a baseline adjustment is applied, baseline is defined as information collected at the randomisation visit (Visit 2), if not otherwise stated. If the assessment is not available at the randomisation visit but at the screening visit (Visit 1) then this will be used instead.

All the analyses specified in the protocol will be reviewed in relation to the blinded data obtained and the statistical analysis plan update will be finalised before breaking the randomisation code.

Any changes from the statistical analysis planned in this clinical trial protocol will be described and justified in the statistical analysis plan update (SAPU) and/or in the clinical trial report dependent on the type of deviation.

For endpoints evaluated over time, plots will be made to explore the trajectory with time.

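### No planned laboratory table counts, by arm, the subjects who crossed the protocol's own lymphocyte and leukocyte limits; the low/normal/high shift at Week 24 does not show severity

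*Combined protocol and SAP*

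**What the plan says.** Section 13.3.8.4 lists three laboratory outputs:

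- Change from baseline to Week 24, "summarised as mean, SD, median, minimum and maximum values for each treatment group".
- A shift table of baseline against Week 24, with each value classed as low, normal or high "depending on whether the value is below, within or above the reference range, respectively".
- A listing of subjects with values outside the reference range.

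Section 10.8.2 sets count limits for the fumarate arm only. Lymphocytes below 0.7 × 10^9/L halve the dose, and treatment stops if the count is still below that level at a check after 4 weeks. Lymphocytes below 0.5 × 10^9/L or leukocytes below 3 × 10^9/L stop treatment. The reason given is that progressive multifocal leukoencephalopathy has occurred with moderate to severe, prolonged lymphopenia.

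On visits, section 13.3.10 says: "An observed-cases approach will be used for tabulations of data by visit (i.e. involving only those subjects who attended each specific visit". Section 9.5.2 says: "The early termination is captured in the eCRF as an unscheduled visit by selecting the early termination option". Note 5 to Panel 2, which concerns the scheduling of follow-up, describes the end of treatment date as "captured at Week 24 or at an early treatment withdrawal visit".

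**The concern.** Section 6.2.2 calls mild lymphocytopenia and leukocytopenia very common with fumaric acid esters and severe lymphocytopenia common. The protocol therefore distinguishes mild from severe, and its dose rules depend on how low the count falls. The shift table removes that distinction: a lymphocyte count just under the reference limit and one below 0.5 × 10^9/L both appear as low.

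The timing adds to this. The stopping rules take subjects with the lowest counts off fumarate, often before Week 24, while the table looks only at Week 24.

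The safety objective in Panel 3 compares the two treatments. A reader will want to know how many subjects per arm reached the levels at which the protocol halves or stops fumarate, and no planned laboratory table says so.

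**Working it through.** The plan states no figure on this point, so the main check is a reading of each planned output against the question.

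| Output | Counts by arm? | Shows depth of a low count? |
|---|---|---|
| Change to Week 24 (13.3.8.4) | No; the minimum is one extreme value | No |
| Shift table (13.3.8.4) | Yes | No; one low class, Week 24 only |
| Out-of-range listing (13.3.8.4) | No | Only subject by subject |
| Adverse event tables (13.3.8.1) | Yes | By the investigator's grade, not by count |
| Disposition (13.3.1) | Yes | No |
| Exposure (13.3.3) | Content not specified | Not specified |

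**Disposition.** Subjects are tabulated as "completing and withdrawn (and reason for withdrawal), by treatment group and in total", but the recorded reasons are "lack of efficacy, AE, withdrawal by subject, lost to follow-up, death, other". None of these identifies a low count.

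**Exposure.** The text is "Relevant exposure, compliance and drug accountability data will be tabulated". Section 10.9.5 has prescribed dose and reasons for deviation recorded, but no table of dose cuts for low counts is promised.

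**Adverse events.** These give partial coverage in the fumarate arm:

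1. Appendix 2 includes among adverse events the reasons for unfavourable, unplanned changes of drug or dose. A halving or stop under section 10.8.2 should therefore be recorded.
2. Section 12.2.1 records the action taken, including dose reduction and drug withdrawal.
3. Section 13.3.8.1 tabulates events leading to withdrawal by preferred term. It lists no summary by action taken.

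In the brodalumab arm no cell-count rule forces a change. There a low count becomes an adverse event mainly if the investigator, who knows the treatment (section 8.3), judges it clinically significant (section 11.6.1.1). Low counts thus reach the adverse event tables by different routes in the two arms.

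**Comparability of a threshold count.** Exclusion criterion 7 applies the limits of 0.7 (lymphocytes) and 3 (leukocytes) to everyone at screening. A later value below either is new since screening in both arms.

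**Subjects with a Week 24 value.** Section 13.1 assumes 50% dropout on fumarate and less than 40% on brodalumab. These inputs reproduce the plan's total response rates: 0.50 × (1 − 0.50) = 25% and 0.80 × (1 − 0.40) = 48%. If early termination values are not mapped to Week 24:

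- fumarate: 102 × 0.50 = 51 subjects;
- brodalumab: at least 102 × 0.60 = 61.2, about 61 subjects.

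If they are mapped, the early stoppers return to the table but sit in the same low class as mild cases. The severity gap remains either way.

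**Possible size.** The documents give no fumarate rates. Assumption: common means 1/100 to under 1/10, as defined for brodalumab in Appendix 6, and severe lies near the protocol limits, which the documents do not state. Then 102 × 0.01 = 1.0 to 102 × 0.10 = 10.2, so about 1 to 10 fumarate subjects.

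Exact (Clopper-Pearson) 95% limits for x of n = 102 are the 0.025 quantile of Beta(x, n − x + 1) and the 0.975 quantile of Beta(x + 1, n − x). For x = 0 the upper limit is 1 − 0.025^(1/102).

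| x/102 | % | 95% CI |
|---|---|---|
| 0 | 0 | 0 to 3.6% |
| 1 | 1.0 | 0.02 to 5.3% |
| 5 | 4.9 | 1.6 to 11.1% |
| 10 | 9.8 | 4.8 to 17.3% |

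Counts of this size support description only.

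**Not checked.** The laboratory rows of Panel 2 are not in the extracted text, so sampling frequency is unknown to us.

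**The case against.** The strongest reply is that the information is largely there. Stops and dose cuts for low counts rest on central laboratory values and should be recorded as adverse events whatever severity grade the investigator assigns. The table of events leading to withdrawal should show the resulting withdrawals by preferred term and arm. With 1 to 10 subjects, a reader can also count from the listing. The named safety endpoint is adverse events by preferred term, which is analysed, and section 13.3.10 foresees a statistical analysis plan update where table details belong. The same section adds the number of non-attenders for categorical endpoints, which might make the missing Week 24 subjects visible.

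Much of this stands, and it makes the point a minor one. It does not close the gap. Adverse event terms carry no count threshold, and in brodalumab no cell-count rule prompts a record. A listing has no denominators. Laboratory classes are not named endpoints, so the non-attender rule may not apply, and it would not show severity anyway. The update is not among the documents reviewed, and the protocol does not promise such a table.

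A second objection concerns the remedy: a worst-value count is not neutral between the arms. The 4-week recheck binds fumarate only, and note 2 to Panel 2 allows unscheduled resampling for abnormal results. More samples can lower the observed minimum in that arm. This is correct, and the fix allows for it.

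**Conclusion.** The point holds as a cheap improvement of minor severity. No planned laboratory table shows by arm how many subjects crossed 0.7, 0.5 or 3 × 10^9/L, and mild and severe low counts share one class. This follows directly from section 13.3.8.4 and needs no assumption. The size of 1 to 10 of 102 fumarate subjects rests wholly on the borrowed frequency convention.

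Three stronger readings are not supported:

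- A reader might infer that early stoppers are certainly missing from the Week 24 shift. That is likely under observed cases with early termination stored as an unscheduled visit. However, note 5 to Panel 2 allows an early visit to supply the end of treatment date, and the plan does not say how such values enter the laboratory table.
- A reader might infer that severe lymphopenia would go unreported. The adverse event tables and the listing should show part of it.
- A reader might infer a risk to subjects or to the main result. The stopping rules operate whatever is tabulated, and the co-primary analyses are untouched.

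**What to change.** Keep the existing outputs. In section 13.3.8.4 or the statistical analysis plan update, add one descriptive by-arm table on the safety analysis set:

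- Number and percentage with worst post-baseline lymphocytes <0.7 × 10^9/L, lymphocytes <0.5 × 10^9/L and leukocytes <3 × 10^9/L, among subjects with at least one post-baseline sample.
- Main rows from scheduled and early termination samples, and a second version that also includes unscheduled samples.
- Exposure time per arm alongside, since the arms may differ in time on treatment.
- A footnote naming both biases: dose-halving and stopping may understate the <0.5 row for fumarate, while fumarate-only 4-week rechecks and extra resampling may lower its observed minimum.

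Also state how early termination values enter the Week 24 shift table.

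The cost is one extra table with small counts and a few lines of text. The data are already collected. No new samples and no change to dosing or stopping rules are needed.
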